3. General Description of Study Design

Retrospective part

Patient characteristics and disease-related (trigger finger) variables will be collected retrospectively from patient charts on EPIC.

Prospective part

This will be a prospective two-arm study. Patients will either be treated with ultrasound-guided trigger finger release or open trigger finger release (conventional method). [name] is the only surgeon within the Mass General Brigham (MGB) hospitals that performs ultrasound-guided trigger finger release. All other surgeons perform open trigger finger releases.

Surgeons will measure range of motion and grip strength preoperatively and during postoperative visits, which is part of routine care. We will also administer questionnaires to see how patients are doing postoperatively. See the '6. Study Procedures' for a more elaborate description of the visits.

4. Subject Selection

Inclusion criteria:

1. ≥ 18 years of age
2. Clinical diagnosis of trigger finger
3. Patient has failed conservative treatment or elects not to undergo conservative treatment
4. Surgeon agrees that surgery is indicated
5. Subject agrees to complete follow-up questionnaires over a 6-month period

Exclusion criteria:

1. Prior surgery on the target finger
2. History of prior surgical pulley release in the target hand
3. History of prior surgical pulley release in the contralateral hand within 3 months of enrollment or with persistent symptoms that interfere with normal daily activities or work at the time of consent
4. Corticosteroid injection in the target finger or hand within 6 weeks of surgery
5. Presence of additional process in the target wrist or hand requiring additional intervention beyond pulley release (e.g., neurolysis, mass removal, tenosynovectomy)
6. Clinically significant trauma or deformity of the upper limb (shoulder to hand) on the target side
7. Clinically significant vascular disease (including Raynaud's phenomenon) of the upper limb (shoulder to hand) on the target side
8. Clinically significant neurological disorder (including complex regional pain syndrome) of the upper limb (shoulder to hand) on the target side
9. Planned surgical or interventional procedure on the contralateral wrist or hand

10. Systemic inflammatory disease (e.g., rheumatoid arthritis, lupus)
11. Amyloidosis
12. Diabetes not controlled by a stable dose of medication over the past three months
13. Pregnant or planning pregnancy in the next 6 months
14. Workers' compensation subjects

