We will include all patients who meet the inclusion criteria. We do not exclude patients based on race, color, national origin, sex, sexual orientation, or religion. We will not enroll vulnerable patient populations in this study.

5. Subject Enrollment

Patients will be prescreened through retrospective manual chart review.

Patients will be contacted in person at one of the MGB hospitals (MGH main campus, MGH Waltham, MGH Danvers, BWH main campus, BWH Faulkner, and BWH Foxborough). Patients who meet the inclusion criteria will get a summary of the study by an orthopedic surgeon or a study staff member to see if they are interested. If patients are interested, they will receive the study fact sheet, and the surgeon or study staff member will explain the study in more detail and answer any questions the patient may have. Subjects will be asked to complete the questionnaire either in person or over email or telephone before surgery. Subjects who opt to not complete the questionnaire in person will be contacted using the email or telephone script approved in this study. Subjects who do not complete the pre-op questionnaire before surgery will be withdrawn. Subjects can opt to receive an encrypted or unencrypted email. Subjects who indicate verbally in the outpatient clinic that they do not wish to participate will not be included in the study.

Depending on the treating surgeon, patients will either be treated with an open trigger finger release or an ultrasound-guided trigger finger release.

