6. STUDY PROCEDURES

Study visits

Visits	Procedures
Visit 1 – before surgery	
- Obtain informed consent- ADL questionnaire (see next section)- Visual analog scale for pain (VAS): pain on a scale of 1 to 10 
The measurements are part of standard care and performed by caregivers
 
- Perform the following measurements: range of motion of the PIP joint of the affected finger (including noting any flexion contracture), distance fingertip to distal palmar crease (DPC), and grip strength using Jamar 2 setting.
Visit/Telephone call 2 (2-4 days after surgery)	
- Take the following questionnaire:
1. Are you able to return to activities of daily living, and what activities do you still have trouble doing? You can list the activities you are having trouble with.2. VAS3. How many oxycodone or other narcotic medications are you taking post-op4. Are you able to return to work?

	
5. Are you satisfied with the procedure, and would you choose to have it again for a similar problem?
 
- Take the ADL questionnaire (see next section)- If in person (part of standard care, only collected by study staff, measurements performed by caregivers): Perform the following measurements: range of motion of the PIP joint of the affected finger (including noting any flexion contracture), distance fingertip to distal palmar crease (DPC), and grip strength using Jamar 2 setting.
Visit/Telephone call 3 (6-8 days after surgery)	
- Take the following questionnaire:
1. Are you able to return to activities of daily living, and what activities do you still have trouble doing? You can list the activities you are having trouble with.2. VAS3. How many oxycodone or other narcotic medications are you taking post-op4. Are you able to return to work?5. Are you satisfied with the procedure, and would you choose to have it again for a similar problem?- Take the ADL questionnaire (see next section)- If in person (part of standard care, only collected by study staff, measurements performed by caregivers): Perform the following measurements: range of motion of the PIP joint of the affected finger (including noting any flexion contracture), distance fingertip to distal palmar crease (DPC), and grip strength using Jamar 2 setting.

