- Range of motion of the PIP joint of the affected finger using a goniometer (in degrees), including any flexion contracture + Distance of fingertip from DPC
- Grip strength in the affected as well as contralateral hand using a dynamometer at Jamar 3 setting (in lbs)
- Return to activities of daily living. One question is: 'What activities can't you do?'. We also take a questionnaire to rate their ability to do certain activities (see questionnaire under this section). Patients can rate their ability to perform each activity on a scale from 1 to 5 (1 indicating no difficulty and 5 indicating unable to perform).
- VAS (a pain scale from 1 – 10, reported by the patient)
- How many oxycodone or other narcotic medications are you taking post-op? The number of pills taken will be given.
- Return to work. Patients give a date of when they started working again. Then we'll calculate the return to work in weeks
- Are you satisfied with the procedure, and would you choose to have it again for a similar problem? Answered with yes or no.
- Complications (i.e., trigger finger recurrence, infection, bleeding, etc.)

ADL questionnaire

Mass General Brigham Institutional Review Board
Intervention/Interaction Detailed Protocol

Opening jar	1	2	3	4	5
Driving	1	2	3	4	5
Household Chores	1	2	3	4	5
Carrying Groceries	1	2	3	4	5
Buttoning	1	2	3	4	5
Bathing	1	2	3	4	5
Cooking	1	2	3	4	5
Writing	1	2	3	4	5
Dressing	1	2	3	4	5
Shopping	1	2	3	4	5
Holding a book	1	2	3	4	5
Eating	1	2	3	4	5
Using a Computer	1	2	3	4	5
Holding a Phone	1	2	3	4	5
Using Toilet	1	2	3	4	5

Description of plans for return of research results as applicable

Not applicable

Definition of primary and secondary outcomes/endpoints

Primary endpoints:

- The 5 questions asked in the section above, together with the *ADL questionnaire*
- Recurrence of trigger finger or incomplete release

Secondary endpoints:

- Range of motion of the PIP joint of the affected finger (including noting any flexion contracture)
- Distance fingertip to distal palmar crease
- Grip strength in the affected hand
- Other complications than recurrence of trigger finger or incomplete release

Local site restrictions or site-specific procedures as applicable

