The visits during the first 3 months are part of standard care. Patients with persistent problems will be seen at the 6-month follow-up as part of standard care. If they are doing well clinically, we will only contact them by phone or email to complete these questionnaires using Redcap (see above for the scheme).

Remuneration as applicable

There is no remuneration for this study.

2. Risks and Discomforts

Trigger finger release is a standard procedure (whether it is open or ultrasound-guided) for a trigger finger.

This study's foreseeable risks and discomforts include the time required to complete the measurements and questionnaires. All electronic information (like measurements in Excel files) will be stored on

password-protected computers in a locked office that only study staff members can access. Study data of the questionnaires will be collected and maintained electronically using REDCap, a secure and HIPAA-compliant web-based application to which only study staff will have access. This limits the risk of a data and confidentiality breach, though it is a possibility.

We do not foresee additional risks for subjects participating in the study. Subjects will receive usual care, regardless of their participation. Physicians will be readily accessible for consultation should a subject experience discomfort while completing the measurements and questionnaires or at any time during the study.

3. Benefits

Patients will not receive any direct benefits from this study. However, their participation will help us to determine clinical outcomes after ultrasound-guided and open trigger finger release, which can help patients and physicians in shared decision-making. Potential benefits of ultrasound-guided trigger finger release could be a faster recovery (faster return to work) and better patient-reported aesthetics.

4. Statistical Analysis

Normally distributed continuous data will be stated as mean \pm standard deviations, non-normally distributed continuous data as medians with interquartile ranges and categorical data as frequencies and percentages.

We plan to statistically compare the postoperative clinical data of open trigger finger release to ultrasound-guided trigger finger release.

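### Return to work is a primary item asked of every patient, but no pre-operative work status, not-applicable answer or analysis set is specified for it

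*Combined protocol and SAP*

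**What the plan says.** All references are to the combined protocol and SAP.

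- **Endpoint.** Section 6, under the definition of endpoints, lists as primary "The 5 questions asked in the section above, together with the" ADL questionnaire. Question 4 of the five is "Are you able to return to work". The visit table repeats it at contacts 2 to 7, from days 2–4 to 6 months.
- **Derived variable.** Section 6, under the data variables, reads: "Return to work. Patients give a date of when they started working again. Then we'll calculate the return to work in weeks".
- **Eligibility.** Section 4, Subject Selection, asks for "≥ 18 years of age" and sets no upper limit. The one work-related criterion excludes "Workers' compensation subjects". The text before section 5 adds: "We will include all patients who meet the inclusion criteria".
- **Baseline.** Visit 1 takes consent, the ADL questionnaire, pain VAS and physical measurements. Section 3 of the design description adds chart data described only as patient characteristics and disease-related variables. Employment is named in neither place.
- **Stated benefit.** The Benefits section says: "Potential benefits of ultrasound-guided trigger finger release could be a faster recovery (faster return to work"), alongside better patient-reported aesthetics.
- **Analysis.** The Statistical Analysis section gives tests for continuous and categorical data. It defines no population, not-applicable category or censoring rule for this item.

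**The concern.** Return to work has meaning only for someone who had work to return to. A retired patient asked question 4 may say no, may give a hypothetical yes because the hand would allow it, or may leave it blank. None of these answers says anything about recovery of working capacity in a job, yet each is collected as a primary outcome.

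Two things could go wrong. If the arms have similar shares of non-workers, a real difference among workers is diluted. If the shares differ, the arms can differ with no effect of technique. Nothing in the design balances the shares: patients are not randomised, and one surgeon performs all the ultrasound-guided releases. The item also bears on a benefit the protocol itself names. Work status before surgery cannot be reliably recovered from a postoperative no, so a gap at Visit 1 is hard to repair at analysis.

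**Working it through.** **1. The plan's own figure.** Inputs from the power analysis: alpha 0.05, power 0.80, effect size d = 0.5, two equal groups. A one-sided two-sample t-test needs 50.15, so 51 per arm and 102 in total, as stated. For non-normal data, 50.15 × π/3 = 52.5, so 53 per arm and 106 in total, as stated. A two-sided t-test would need 64 per arm. The plan does not state sidedness. These totals are said to cover the five questions, and they count every enrolled patient as evaluable.

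**2. Yes/no item: formula.** Let w be the share employed before surgery, p the share of workers answering yes, and q the share of non-workers answering yes. The observed share is

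w × p + (1 − w) × q.

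The documents give none of w, p or q, so all values below are assumptions.

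**3. Dilution.** With equal w and q in both arms, the observed difference is w × (p₁ − p₂). Take 70% versus 50% among workers:

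- 40% non-workers, all answering no: 0.6 × 70% = 42% and 0.6 × 50% = 30%, a difference of 12 points, not 20.
- 20% non-workers: 0.8 × 20 = 16 points.

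The shrinkage is the same if all non-workers answer yes, because q cancels.

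**4. Case mix.** With no technique effect (p₁ = p₂ = p) and equal q, the observed difference is (w₁ − w₂) × (p − q).

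- w = 60% versus 50%, p = 100%, q = 0: 10 points. At 51 per arm this is about 31 versus 26 patients, uncorrected chi-squared p about 0.32.
- w = 70% versus 50%, p = 70%, q = 0: 14 points, declared significant in that direction about 30% of the time (two-sided test).
- p = q: no spurious difference at all.

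**5. Does restriction to workers pay?** Assume 70% versus 45% yes among workers, 51 per arm, two-sided test.

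| Situation | Power |
|---|---|
| Everyone works | 0.73 |
| 40% non-workers, all answer no (42% v 27%) | 0.36 |
| 40% non-workers, all answer yes (82% v 67%) | 0.41 |
| Same, restricted to workers (about 31 per arm) | 0.51 |

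Restriction does better than either mixed analysis despite the smaller n.

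**6. Weeks variable.** A patient without a job gives no restart date, so has no value and drops out of a t-test or Mann-Whitney comparison. A worker who has not gone back by 6 months also has no date. Without baseline status the two look identical.

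**7. Cost of restriction at d = 0.5.** Workers per arm = 51 × w.

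| w | Per arm | Power, one-sided | Power, two-sided | Enrolment per arm to keep 51 workers |
|---|---|---|---|---|
| 1.0 | 51 | 0.81 | 0.71 | 51 |
| 0.8 | about 41 | 0.72 | 0.61 | 64 |
| 0.6 | about 31 | 0.61 | 0.49 | 85 |
| 0.4 | about 20 | 0.47 | 0.34 | 128 |

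**The case against.** The strongest reply is that the only definition of the variable is a date turned into weeks: "Patients give a date of when they started working again". The satisfaction item in the same list is marked as a yes/no answer; return to work is not. On that reading non-workers simply have no value. This stands for the weeks variable. A reader might infer that every non-worker is counted as a failed return, and the documents do not support that. What remains there is the inability to separate non-workers from workers who never returned. The yes/no comparison is still open, because question 4 is worded that way and is primary.

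A second reply is that silence is not absence. The REDCap form is not in the documents, and the chart characteristics are not itemised. A reader might infer that work status is not collected at all; the documents show only that none is specified. Even if it is in the chart, no analysis is said to use it.

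A third reply is that the magnitudes rest on assumed shares, and that case mix is one instance of the general confounding from surgeon-based allocation. Both are true. A reader might conclude that the return-to-work result will be biased by a known amount or towards one technique; neither size nor direction can be derived from the documents. Unlike most confounding, though, this part can be removed by one baseline question.

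**Conclusion.** The concern holds as a gap in defining who the endpoint applies to. A primary item is put to all patients, the plan does not identify those to whom it cannot apply, and allocation does not balance them. The effect on the yes/no item is dilution in proportion to the non-working share (20 points becoming 12 or 16 under the assumed 40% or 20%) and a possible case-mix difference if the shares differ between arms. The effect on the weeks variable is ambiguity about missing dates. The true size is unknown. The point concerns one of several primary items and does not touch the ADL, pain or recurrence outcomes. The change is worth making because it is cheap and because the information may not be recoverable later.

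**What to change.** 1. Add one item to the Visit 1 questionnaire on employment status before surgery: *employed and working* / *employed but on leave, including because of the finger* / *not employed, including retired or homemaker*. The on-leave category keeps in the analysis those for whom return to work may matter most.
2. Add *does not apply, not employed before surgery* to question 4.
3. State in the Statistical Analysis section that both return-to-work comparisons, yes/no and weeks, are restricted to patients employed before surgery. Those not back by 6 months count as not returned in the first and are censored in the second. The listed t-test and Mann-Whitney test do not handle censoring, so name a time-to-event comparison such as the log-rank test.
4. State in the power analysis that the stated power does not apply to this item at 51 per arm, and report its n separately. If 60% work, about 31 per arm remain, with power at d = 0.5 of about 0.61 one-sided or 0.49 two-sided.

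Eligibility and the other endpoints stay as they are. The cost is one REDCap question, one response option and a few sentences, plus a smaller n for return to work. Capture should be nearly complete, because patients who do not complete the pre-operative questionnaire are already withdrawn (section 5, Subject Enrollment).

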We will use a student t-test to analyze normally distributed continuous data. When we compare data at two different time points within a group, we will use a paired student t-test. When we compare continuous data of two different groups, we will use an unpaired student t-test.

We will use a Mann-Whitney U test if the continuous data is not normally distributed.

We will use Fischer's exact test or a Chi-squared test for differences in categorical variables, depending on the number of events in the different groups.

Power analysis

We have performed a power analysis to find differences between two independent means (normally distributed) with alpha = 0.05, power = 0.80, and effect size 0.5. This would require a total sample size of 102 patients (51 in each group). If the data is non-normally distributed with the same alpha, power, and effect size, we would need a total of 106 patients (53 in each group).

This power analysis is performed for our most important primary outcomes: the 5-question and ADL questionnaires.

5. Monitoring and Quality Assurance

The full-time research coordinator and principal investigator are responsible for adherence to all IRB policies and guidelines and for the accuracy and completeness of all forms, entries, and informed consent.

Study data will be maintained in a locked filing cabinet and/or on password-protected computers. Questionnaires and self-reported responses will not become part of the subject's medical record. Hard copies of study-related data and forms will be stored in a lockable file cabinet. Only the investigators and study staff will have access to this information. Any magnetic or electronic information will be saved in password-protected computers, which only study staff members can access. REDCap, secure and HIPAA-compliant, will be used to collect all answers.

For guidance, refer to the following Partners policies:

Data and Safety Monitoring Plans and Quality Assurance

https://partnershealthcare-public.sharepoint.com/ClinicalResearch/DSMP_in_Human_Subjects_Research.pdf

Reporting Unanticipated Problems (including Adverse Events)

https://partnershealthcare-public.sharepoint.com/ClinicalResearch/Reporting_Unanticipated_Problems_including_Adverse_Events.pdf

6. Privacy and Confidentiality

- Study procedures will be conducted in a private setting
- Only data and/or specimens necessary for the conduct of the study will be collected

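### The primary ADL form does not say whether to rate usual performance or the treated hand, and hand dominance is neither listed as a variable nor adjusted for in the non-randomised comparison

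*Combined protocol and SAP*

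**What the plan says.** The ADL form appears in section 6 (Study Procedures), under the data variables to be collected. It has 15 activities, each scored 1 to 5, with "1 indicating no difficulty and 5 indicating unable to perform". The sentence that introduces it is "Patients can rate their ability to perform each activity on a scale from 1 to 5". Neither that sentence nor the printed form mentions a hand, and there is no option for a task done with the other hand. In the same list, grip is specific: "Grip strength in the affected as well as contralateral hand using a dynamometer".

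The form is a primary endpoint ("The 5 questions asked in the section above, together with the" ADL questionnaire), and the Power analysis paragraph names it among "our most important primary outcomes: the 5-question and ADL questionnaires". It is given before surgery at Visit 1 and at all six later contacts, which may be in person, by telephone or by e-mail.

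Dominance or handedness is not mentioned in the eligibility criteria, the visit table, the variable list or the Statistical Analysis section. The one place that could cover it is section 3: "Patient characteristics and disease-related (trigger finger) variables will be collected retrospectively from patient charts on EPIC". Those characteristics are not itemised.

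Sections 2 and 5 say that patients are not randomised and that the operation depends on the treating surgeon. The Statistical Analysis section plans a comparison of postoperative data between arms by t-test, Mann-Whitney, or Fisher/chi-squared test. It names no covariate.

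**The concern.** Two things are left open on a primary endpoint.

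The first is what is being rated. Without a fixed instruction, one patient may rate the task as usually done and another the treated hand. The same patient may also switch between contacts, especially when the mode changes from clinic to telephone to e-mail.

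The second is dominance. Writing, and often eating, is done mainly with the dominant hand. A patient treated on the other hand may score near 1 on these items before and after surgery. Such items then say little about the operation in that patient, and the patient's total is lower (better) than that of an equally recovered patient treated on the dominant hand. In a randomised trial this would mostly be noise. Here, if one surgeon's patients include more non-dominant hands, that arm would look better on ADL for a reason unrelated to technique, and the planned tests cannot separate the two.

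**Working it through.** **The plan's own figure.** Inputs from the Power analysis paragraph: alpha 0.05, power 0.80, effect size 0.5, 51 per group (53 if non-normal). With the noncentral t distribution, 51 per group gives power 0.806 one-sided and 0.706 two-sided. The Mann-Whitney size with efficiency 3/π is 53 per group one-sided. So 102 and 106 reproduce as one-sided sizes; the paragraph does not state sidedness. The starting point below is one-sided power 0.81 at d = 0.50.

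**Assumed inputs (none is in the documents).**
- p, share treated on the non-dominant hand: 0.4 to 0.5
- k, items of the 15 that stay at 1 in those patients: 3 to 6
- ρ, inter-item correlation: 0.3 to 0.7
- m, mean difference per affected item between dominant- and non-dominant-hand patients: 0 to 1 item SD for dilution, 0.5 to 1 for bias
- Δ, between-arm difference in the share of non-dominant hands: 0.10 to 0.20
- items summed with equal SDs (set to 1); the protocol gives no scoring rule

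**Dilution.** The mean difference shrinks by the factor 1 − pk/15. The variance changes too, because items stuck at 1 contribute none:
- V1 (all items responsive) = 15 + 15·14·ρ = 78 at ρ = 0.3; 162 at ρ = 0.7
- V2 (k items stuck) = (15−k) + (15−k)(14−k)ρ
- V (mixture) = (1−p)V1 + pV2 + p(1−p)(km)²
- d = 0.5 × (1 − pk/15) × √(V1/V)

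Mild end (p = 0.4, k = 3, ρ = 0.7, m = 0): V2 = 12 + 132 × 0.7 = 104.4; V = 0.6 × 162 + 0.4 × 104.4 = 138.96; d = 0.5 × 0.92 × √(162/138.96) = 0.497; one-sided power 0.80.

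Severe end (p = 0.5, k = 6, ρ = 0.3, m = 1): V2 = 9 + 72 × 0.3 = 30.6; V = 0.5 × 78 + 0.5 × 30.6 + 0.25 × 36 = 63.3; d = 0.5 × 0.80 × √(78/63.3) = 0.444; one-sided power 0.72.

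Over all ρ and m, p = 0.4 with k = 3 gives d 0.49 to 0.50 and power 0.79 to 0.80; p = 0.5 with k = 6 gives d 0.44 to 0.48 and power 0.72 to 0.78.

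**Imbalance.** Bias in SD units = k·m·Δ / √V1.
- Smallest: 3 × 0.5 × 0.10 / √162 = 0.15/12.73 = 0.012
- Largest: 6 × 1 × 0.20 / √78 = 1.2/8.83 = 0.136

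Dividing by the smaller mixture SD (√63.3 = 7.96) raises the largest value to 0.15. As for whether Δ is plausible: by chance alone, with 51 per arm and p = 0.4, the SD of the difference in shares is √(2 × 0.4 × 0.6/51) = 0.097. An imbalance of 10 to 20 points is therefore about one to two chance SDs, before any difference in case mix between surgeons.

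**The case against.** Much of the case on the other side stands.

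- A reader might infer that dominance is not collected. The documents do not show that. The list in section 6 covers outcomes and omits age and sex as well, and the chart characteristics in section 3 could include dominance. The supportable statement is that it is not listed and no planned analysis uses it. The treated side must be known, since grip is taken in the affected and contralateral hands.
- A reader might infer that patients treated on the non-dominant hand score one-handed tasks as easy whatever the operation achieved. Nothing in the documents shows this. Opening a jar, buttoning, dressing, cooking and household chores usually need both hands, and a phone or book is often held in the non-dominant hand.
- A reader might infer a large loss of power. Holding the SD fixed gives d = 0.5 × 0.92 = 0.46 and 0.5 × 0.80 = 0.40, with one-sided power 0.75 and 0.64. That shrinks the signal but not the noise. It also assumes that the planned 0.5 refers to an ideal, fully responsive score rather than the form as used.
- Rating overall ability is a legitimate construct: a patient who can write has truthfully no difficulty writing. This stands, but the form should then say that this is what is wanted.
- The Visit 1 ADL score would reveal items already at 1. This is true, but the planned between-arm test does not use it. It is also only a partial substitute: a patient with mild disease in the dominant hand can also score 1 on writing before surgery, yet find writing hard in the days after it.
- Nothing links surgeon to treated-hand dominance, and dominance is one of several unadjusted factors. This is fair. It is singled out because it bears directly on what the primary form measures.

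**Conclusion.** The point holds as a cheap improvement, not as a serious flaw. The form leaves the rated hand open, dominance is not listed, and the unadjusted comparison in surgeon-determined arms would absorb any imbalance in dominant-hand surgery. Under the assumed inputs the bias is roughly 0.01 to 0.14 SD, at most a little over a quarter of the planned 0.5 (0.136/0.5 = 0.27). Dilution by itself is minor. These sizes rest wholly on assumptions, and the true values could lie outside the ranges. The main gains from a change are consistent answers across patients and contacts, and protection against imbalance; recovered power is secondary.

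**What to change.** 1. Record hand dominance at Visit 1 and, with the treated side, derive dominant-hand surgery (yes/no). For patients already enrolled, take dominance from the chart or by one question at the next contact.
2. Put one fixed instruction at the head of the ADL form, identical at every contact and in every mode. Asking patients to rate the task as usually done would keep the present construct.
3. Compare postoperative ADL between arms with a model adjusted for dominant-hand surgery and the Visit 1 ADL score, and state in the Statistical Analysis section how the 15 items are combined.

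The cost is one baseline field, one header line in REDCap and on the telephone and mailed versions, and one or two covariates. The downside is that answers given before the header was added may be less consistent with later ones. The date of the change should be recorded so that this can be examined.
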